5.2.3 Screening Criteria

There are no screening criteria other than the inclusion and exclusion criteria.

5.2.4 Inclusion Criteria

An individual must fulfill *all* of the following criteria in order to be eligible for trial enrollment:

- 1) Has been identified as a potential subject by the Sponsor, and is included in the list provided to the Investigator (i.e., aged 9 to 45 years on the day of first injection of CYD dengue vaccine in CYD28, has received 3 doses of CYD dengue vaccine in the CYD28 trial, and has a PD3 serum sample available [at least 300 µL of serum]).

- 2) Presently in good health, based on medical history and physical examination.
- 3) Informed consent form (ICF) has been signed and dated by the subject (based on local regulations), and ICF has been signed and dated by the parent(s) or another legally acceptable representative (and by an independent witness if required by local regulations)
- 4) Subject and parent(s)/legally acceptable representative(s) able to attend all scheduled visits and to comply with all trial procedures

5.2.5 Exclusion Criteria

An individual fulfilling *any* of the following criteria is to be excluded from trial enrollment:

- 1) Subject who received any other dengue vaccination that was not part of CYD28
- 2) Subject is pregnant, or lactating, or of childbearing potential (to be considered of non-childbearing potential, a female must be pre-menarche or post-menopausal for at least 1 year, surgically sterile, or using an effective method of contraception or abstinence from at least 4 weeks prior to the vaccination until at least 4 weeks after vaccination)
- 3) Participation at the time of study enrollment (or in the 4 weeks preceding the trial vaccination) or planned participation during the present trial period in another clinical trial investigating a vaccine, drug, medical device, or medical procedure
- 4) Receipt of any vaccine in the 4 weeks preceding the trial vaccination or planned receipt of any vaccine in the 4 weeks following the trial vaccination
- 5) Receipt of immune globulins, blood or blood-derived products in the past 3 months
- 6) Known or suspected congenital or acquired immunodeficiency; or receipt of immunosuppressive therapy, such as anti-cancer chemotherapy or radiation therapy, within the preceding 6 months; or long-term systemic corticosteroid therapy (prednisone or equivalent for more than 2 consecutive weeks within the past 3 months)
- 7) Known systemic hypersensitivity to any of the vaccine components, or history of a life-threatening reaction to the vaccines used in the trial or to a vaccine containing any of the same substances
- 8) Chronic illness that, in the opinion of the Investigator, is at a stage where it might interfere with trial conduct or completion
- 9) Receipt of blood or blood-derived products in the past 3 months, which might interfere with assessment of the immune response
- 10) Deprived of freedom by an administrative or court order, or in an emergency setting, or hospitalized involuntarily
- 11) Current alcohol abuse or drug addiction
- 12) Moderate or severe acute illness/infection (according to investigator judgment) on the day of vaccination or febrile illness (temperature $\geq 38.0^{\circ}\text{C}$). A prospective subject should not be included in the study until the condition has resolved or the febrile event has subsided
- 13) Identified as an Investigator or employee of the Investigator or study center with direct involvement in the proposed study, or identified as an immediate family member (i.e., parent, spouse, natural or adopted child) of the Investigator or employee with direct involvement in the proposed study

If the subject has a primary physician who is not the Investigator, the site should contact this physician with the subject's consent to inform him / her of the subject's participation in the study. In addition, the site should ask this primary physician to verify exclusion criteria relating to previous therapies, such as receipt of blood products or previous vaccines.

5.2.6 Medical History

Prior to enrollment, subjects will be assessed for pre-existing conditions and illnesses, both past and ongoing. Any such conditions will be documented in the source document. Significant medical history (reported as diagnosis) including conditions for which the subject is or has been followed by a physician or conditions that could resume during the course of the study or lead to an SAE or to a repetitive outpatient care will be collected in the CRF. The significant medical history section of the CRF contains a core list of body systems and disorders that could be used to prompt comprehensive reporting, as well as space for the reporting of specific conditions and illnesses.

For each condition, the data collected will be limited to:

- Diagnosis (this is preferable to reporting signs and symptoms)
- Presence or absence of the condition at enrollment

The reporting of signs and symptoms is strongly discouraged.

Dates, medications, and body systems are not to be recorded, and the information collected will not be coded. Its purpose is to assist in the later interpretation of safety data collected during the trial.

5.2.7 Contraindications for Subsequent Vaccinations

5.2.7.1 Temporary Contraindications

Should a subject experience one of the conditions listed below, the Investigator will postpone the vaccination until the condition is resolved.

- Febrile illness (temperature $\geq 38.0^{\circ}\text{C}$) or moderate or severe acute illness / infection on the day of vaccination, according to Investigator judgment

5.2.7.2 Definitive Contraindications

Not applicable since only one dose of vaccine will be administered in this trial.

5.2.8 Conditions for Withdrawal

Subjects (and subjects' parent(s) / legally acceptable representative(s) for subjects aged < 21 years) will be informed that they have the right to withdraw (or to withdraw their child) from the trial at any time. A subject may be withdrawn from the study:

- At the discretion of the Investigator or Sponsor due to safety concerns (withdrawal) without the subject's permission
- At the request of the subject (dropout)

The following will result in automatic withdrawal or exclusion of a subject from the study:

- Significant non-compliance with the protocol, based on the Investigator's judgment

The reason for a withdrawal or dropout should be clearly documented in the source documents and on the CRF.

The Investigator must determine whether voluntary withdrawal is due to safety concerns (in which case, the reason for discontinuation will be noted as "SAE" or "other AE" as appropriate) or for another reason.

Withdrawn subjects will not be replaced.

5.2.9 Lost to Follow-up Procedures

In the case of subjects who fail to return for a next visit, documented reasonable effort (i.e., documented telephone calls and certified mail) should be undertaken to locate or recall them, or at least to determine their health status while fully respecting their rights. These efforts should be documented in the CRF and in the source documents.

5.2.10 Classification of Subjects Who Discontinue the Trial

For any subject who discontinues the trial prior to completion, the most significant reason for early termination will be checked in the CRF. Reasons are listed below from the most significant to the least significant (refer to the CRF completion guidelines for additional details and examples):

- **SAE:** To be used when a subject drops out of or is withdrawn from the study by the Investigator because of the occurrence of an SAE, as defined in [Section 9.2.2.1](#).
- **Other AE:** To be used when a subject drops out of or is withdrawn from the study by the Investigator because of the occurrence of an AE other than an SAE, as defined in [Section 9.2.2.1](#).
- **Non-compliance with protocol:** To be used when the Investigator withdraws a subject from the study because of failure to follow the protocol, including when it is retrospectively discovered that a subject did not fulfill the eligibility criteria. The Investigator will provide a comment as to the specific cause of non-compliance.
- **Lost to follow-up:** To be used when the Investigator withdraws a subject from the study because of failure to establish contact, as outlined in [Section 5.2.9](#). The Investigator will provide documentation that contact was attempted (i.e., return of unsigned certified letter receipt).
- **Voluntary withdrawal not due to an AE:** To be used when a subject drops out of the study for any reason other than those listed above.

5.2.11 Follow-up of Discontinuations

The site should complete all scheduled safety visits and contact any subject who has prematurely terminated the trial because of an SAE, other type of AE, non-compliance with the protocol, or loss of eligibility, including definite contraindications.

For subjects where the reason for early termination was lost to follow-up or if the subject withdrew informed consent and specified that they do not want to be contacted again and it is documented in the source document, the site will not attempt to obtain further safety information.

For subjects where the reason for early termination is voluntary withdrawal, the site will attempt to contact them in order to obtain further safety information, except if the subject specifies that he does not want to be contacted anymore and this will be documented in the source document.

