9.2.2.3.2 Reactogenicity (Solicited Reactions From Day 0 to Day 7/Day 14 After Vaccination)

After vaccination, subjects (or subjects' parent / legally acceptable representative for subjects aged < 21 years) will be provided with a safety DC, a MA, a digital thermometer, and a flexible ruler, and will be instructed how to use them. The following items will be recorded by the subjects (or subjects' parent / legally acceptable representative for subjects aged < 21 years) in the DC on the day of vaccination and for the next 14 days (i.e., D0 to D14) until resolution:

- Daily temperature, with the route by which it was taken
- Daily measurement or intensity grade of all other solicited injection site and systemic reactions
- Action taken for each event, if any (e.g., medication)

The action taken by the subject (or subjects' parent / legally acceptable representative for subjects aged < 21 years) to treat any solicited reactions will be classified in the CRF using the following scale:

- 0: None
- 1: Medication (self-medication with an existing prescription or over-the-counter medication)
- 2: Health care provider contact (no new medication prescribed)
- 3: Health care provider contact and prescription of a new medication (health care provider instructed subject to take a new medication, either an over-the-counter medication or one requiring a written prescription)
- 4: Hospitalization (inpatient)

Subjects (or subjects' parent(s) / legally acceptable representative(s) for subjects aged < 21 years) will be contacted by telephone 2, 4, 8, 10, 14, 16, 18, 20 and 22 months after the vaccination to remind them to record all safety information in the DC.

If the timing of the telephone call should fall on a weekend or a holiday, the call should be made on the next business day. If contact is not made on the designated day, study staff will continue

calling until contact is made. Every telephone attempt and its outcome will be documented in the source document.

[Table 9.1](#) and [Table 9.2](#) present, respectively, the injection site reactions and systemic reactions that are prelisted in the diary cards and CRF, together with the intensity scales.

Table 9.1: Solicited injection site reactions: terminology, definitions, and intensity scales for adolescents and adults (aged 12 >= years)

CRF term (MedDRA lowest level term [LLT])	Injection site pain	Injection site erythema	Injection site swelling
Diary card term	Pain	Redness	Swelling

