4.4.5.4 Subject Duration

The duration of a subject participation in the study is computed as follows:

Maximum (Visit dates, Termination date, Follow-up date, Last contact date) – V01 date + 1.

5 Statistical Methods and Determination of Sample Size

The analysis will be performed under the responsibility of the Sponsor’s Biostatistics platform with the SAS software, version 9.2 or higher (SAS Institute, Cary, North Carolina, USA).

The results of the statistical analysis will be available in the final clinical study report (CSR).

For descriptive purposes, the following statistics will be presented:

Table 5.1: Descriptive statistics produced

Baseline characteristics and follow-up description	Categorical data	Number of subjects. Percentage of subjects.
	Continuous data	Mean, standard deviation, quartiles, minimum, and maximum.
Clinical safety results	Categorical data	Solicited reactions: Number and percentage (95% confidence interval [CI]) of subjects. Unsolicited AEs and SAEs: Number and percentage (95% CIs) of subjects, and number of events. Hospitalized virologically-confirmed dengue case: Number and percentage (95% CIs) of subjects
Immunogenicity results	Categorical data (cutoff)	Number and percentage (95% CIs) of subjects.
	Continuous data (titer / titer ratio)	Log10: Mean and standard deviation. Anti-Log10 (work on Log10 distribution, and anti-Log10 applied): Geometric mean, 95% CI of the geometric mean, quartiles, minimum, and maximum. Graphical representation by Reverse Cumulative Distribution Curve (RCDC).
CMI, Ab specificity and affinity maturation	Categorical data	Number and percentage of subjects above or equal to the LLOD, between some ranges of values and number and percentage (95% CIs) of responders subjects.
	Continuous data	Log10: Mean and standard deviation. Distribution: Geometric mean, 95% CI of the geometric mean, quartiles, minimum, and maximum of the corrected values

The CI for the single proportion will be calculated using the exact binomial method (Clopper-Pearson method, quoted by Newcombe (2), i.e., using the inverse of the beta integral with SAS®).

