5.1.2.2.2 Safety

Safety profile will be described after booster vaccination with CYD dengue vaccine.

The safety analysis will address the number and percentage of subjects with injection site reactions (pain, erythema, and swelling) from D0 and D07, solicited systemic reactions (fever, headache, malaise, myalgia, and asthenia) from D0 to D14, unsolicited AEs until D28, non-serious AESIs (hypersensitivity/allergic reactions) from D0 to D07, and unsolicited immediate systemic event occurring within 30 minutes after a booster CYD dengue vaccine dose. Solicited injection site reactions or solicited systemic reactions will be described according to time of onset, number of days of occurrence, action taken, and intensity.

Unsolicited AEs or non-serious AESIs will be described according to nature (MedDRA SOC, and PT), time to onset, duration, intensity, action taken, and relationship to vaccination.

Unsolicited immediate systemic events will be described according to nature (MedDRA SOC, and PT) and relationship to vaccination.

The number and percentage of subjects with SAEs, including serious AESIs will be described according to nature (MedDRA SOC, and PT), seriousness criteria, outcome, and relationship to vaccination throughout the trial.

All AEs leading to study termination will be described according to nature (MedDRA SOC, and PT) and relationship to vaccination.

The exact binomial distribution (Clopper-Pearson method) for proportions will be used in calculations of the 95% CIs.

Detection of hospitalized virologically-confirmed dengue cases

The number and percentage of subjects with a hospitalized virologically-confirmed dengue cases occurring at any time throughout the trial after the injection will be described using safety analysis set (SafAS).

The 95% CIs for percentages will be calculated using the exact binomial distribution (Clopper-Pearson's method).

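### Sites stop seeking safety information from subjects lost to follow-up who never refused contact, and the 24-month dengue and SAE percentages make no allowance for the unobserved time

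*Protocol*

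**What the plan says.** **Protocol, contact rules.** Section 5.2.9 is triggered by a missed visit ("In the case of subjects who fail to return for a next visit") and then sets out what the site must do before giving up: "documented reasonable effort (i.e., documented telephone calls and certified mail) should be undertaken to locate or recall them". Section 5.2.10 lets the Investigator withdraw a subject as lost to follow-up "because of failure to establish contact, as outlined in" 5.2.9. Section 5.2.11 then provides: "For subjects where the reason for early termination was lost to follow-up or if the subject withdrew informed consent" (the withdrawal limb also requires a documented wish not to be contacted), "the site will not attempt to obtain further safety information". The same section has sites pursue voluntary withdrawals unless they decline contact.

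The footnote to V05 in the protocol's Table of Study Procedures says that subjects who leave early will be phoned for the six-month safety follow-up. It makes no exception for lost to follow-up. The corresponding table in the SAP (Table 3.1) does not carry this footnote.

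**Analysis.** Under the Safety heading of SAP 5.1.2.2.2, the number and percentage of subjects with hospitalized confirmed dengue "occurring at any time throughout the trial after the injection will be described using safety analysis set (SafAS"). The SafAS is everyone injected, with no follow-up condition (Protocol 12.2.3, SAP 5.2.3). SAEs are also summarized as counts and percentages, and the general rule in SAP 5.2.5 puts them on the same set. SAP 4.4.2.3.2 ends the SAE follow-up period at last contact. SAP 4.4.5.4 derives each subject's duration ("The duration of a subject participation in the study is computed as follows"), but no safety rate uses it.

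**The concern.** A subject who cannot be found has not asked to be left alone. Yet 5.2.11 relieves the site of any later attempt, while a subject who chose to leave must still be pursued. A site with a subject lost before Month 6 cannot follow both 5.2.11 and the V05 footnote.

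The analysis then does nothing with the gap. The subject stays in the denominator for all 24 months, although observation stopped earlier. Hospitalized confirmed dengue and SAEs are the safety endpoints that run to Month 24, and the resulting error is always in the reassuring direction. Solicited reactions are handled differently: SAP 4.4.2.1.3 drops subjects without data from the denominator.

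**Working it through.** **Inputs from the documents.** 195 and 65 subjects, with 24 months of follow-up each, so 260 × 2 = 520 planned person-years, of which Group 1 contributes 390. The only attrition figure is the 10% without valid immunogenicity results (Protocol 12.5, SAP 5.5), which is not a rate of loss to safety follow-up.

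**The plan's own safety figure.** The probability of at least one AE at a true incidence of 1.7% in 176 subjects is 1 − (1 − 0.017)^176 = 0.951. This agrees with the stated value of about 95%.

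**Assumptions.** A share L is lost, event incidence is constant, loss is unrelated to risk, and lost subjects report no events spontaneously.

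**Share of person-time unobserved.** L × (24 − m)/24 for loss at month m. Evenly spread losses have mean m = 12. Day 28 is m = 28/30.4375 = 0.92.

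| L (assumed) | Even loss | All at Day 28 |
|---|---|---|
| 2% | 1.0% | 1.9% |
| 5% | 2.5% | 4.8% |
| 10% | 5.0% | 9.6% |
| 20% | 10.0% | 19.2% |

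At L = 10%, that is 26 or about 50 of the 520 person-years. For rare events, the relative shortfall in the crude percentage is practically the same as these shares.

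**Worked example: true two-year risk R = 1.7% (illustrative), L = 10%.** The monthly hazard is h = −ln(1 − 0.017)/24, so 24h = 0.017146. Crude percentage = (1 − L)R + L × (risk accrued before loss).

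- Even loss: the mean accrued risk is 1 − 0.017/0.017146 = 0.0085. The crude value is 0.0153 + 0.00085 = 1.62%.
- All at Day 28: the accrued risk is 1 − exp(−0.92h) = 0.0007. The crude value is 0.0153 + 0.00007 = 1.54%.

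In 195 subjects, the even-loss shortfall is about 0.17 of an event.

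**Zero events, upper Clopper-Pearson limit** = 1 − 0.025^(1/N), with N scaled to observed person-time at L = 10%:

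| | Full N | Even loss | All at Day 28 |
|---|---|---|---|
| Group 1 | 195: 1.87% | 185.25: 1.97% | 176.2: 2.07% |
| Group 2 | 65: 5.52% | 61.75: 5.80% | 58.7: 6.09% |

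**The same case per person-year.** The exact Poisson upper limit with no events is −ln(0.025)/person-years = 3.689/person-years. For Group 1 this is 3.689/390 = 0.95 per 100 person-years with full follow-up, 3.689/370.5 = 1.00 with even loss, and 3.689/352.5 = 1.05 with all losses at Day 28.

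**The case against.** The best defence is that a lost subject has, by definition, already been sought. Sections 5.2.9 and 5.2.10 allow the class only after documented calls and certified mail have failed, so much of the later time could stay unobserved whatever 5.2.11 says. This stands. It does not excuse the rule, because failure at one point does not show that contact would fail for the rest of the trial. Section 5.2.9 sets no minimum number of attempts and no waiting period. A subject classed as lost after the Month 6 visit is missed still has seven planned calls (PC3 to PC9) and two visits ahead.

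It is also fair that crude percentages on all injected subjects are a conventional summary, that these endpoints are descriptive, and that disposition tables are planned. Subjects are told to contact the Investigator if hospitalized for suspected dengue (Protocol 5.1.3) and to notify the site of an SAE (5.1.4), so some events would still surface. Nothing stops a site receiving such a report.

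A reader might infer four stronger points that the documents do not support:

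- **One missed visit ends all contact.** A missed visit starts a search; it does not classify the subject, and no deadline for classification is set.
- **5.2.11 contradicts the phone-call rule in 9.2.2.3.2** ("If contact is not made on the designated day, study staff will continue" calling). That rule concerns scheduled calls to subjects still in the trial, whereas 5.2.11 applies after termination. The genuine conflict is with the V05 footnote.
- **All the person-time computed above is forfeited by 5.2.11.** It is all time after loss. Only the part that further calls would regain is due to the rule, and the documents give no basis for estimating that part.
- **5.2.11 also discards later antibody titers.** The section concerns safety information only; samples are missed because the subject has been withdrawn.

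**Conclusion.** The point holds at modest size. The no-contact rule covers people who did not refuse contact and disagrees with the V05 footnote for anyone terminated before Month 6. Separately, the 24-month dengue and SAE percentages use a fixed denominator with no allowance for incomplete follow-up, so they are biased downward whenever anyone is lost and unreported events are possible.

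At an assumed 10% loss, the bias is about 5% to 10% in relative terms, and it scales with the loss rate. This rests on constant incidence, loss unrelated to risk and no spontaneous reports. Spontaneous reports would shrink the bias; loss caused by illness would enlarge it. Equal loss in both groups would leave their ratio largely unchanged, but unequal loss would distort the comparison. No hypothesis test is affected.

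**What to change.** **(a) Protocol.** In 5.2.11, apply the no-contact rule only to documented refusal. For subjects who cannot be reached, keep attempting the calls already scheduled and the final visit. Align the V05 footnote with this. Reword 5.2.10 so that lost to follow-up becomes final only when the Month 24 window closes without contact; otherwise the withdrawal itself still ends the attempts.

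**(b) SAP, Safety part of 5.1.2.2.2.** Beside each SafAS percentage, report hospitalized confirmed dengue and follow-up-period SAEs per person-year with an exact Poisson 95% CI, by group. Count time to first event or last contact, starting at injection for dengue and at Day 28 for follow-up SAEs. The duration in SAP 4.4.5.4 cannot be used unchanged: it takes the latest of several dates, including the termination date, which can fall after the last contact. For lost subjects it should be cut at last contact.

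**Cost.** A few extra call attempts for the few subjects concerned, small wording changes in the protocol, and one added table row. Part (b) uses dates already collected and is worth making even if (a) recovers nobody.
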